### 8. Research Setting

The study will be performed at the University of New Mexico Hospital (UNMH) and Sandoval Regional Medical Center (SRMC) associated urogynecology clinics. Potential subjects

**PROTOCOL TITLE: SQEASI: Systematized Quality Exercise Alternatives for Stress Incontinence**

will be recruited in the UNM Eubank and SRMC clinic. All patients will have a complete history and physical taken. They will undergo a pelvic exam where they will be instructed on how to perform a pelvic floor contraction correctly and a cough stress test will be performed as part of the standard of care. After recruitment, they will undergo the consent process, and fill out initial questionnaires in the outpatient offices. Patients randomized to the biofeedback group will be given their devices in clinic and research staff will assist in setting up the device and downloading the phone app. The patients randomized to physical therapy will have their PFPT at the UNM Eubank clinic. To standardize therapy for these women all of our pelvic floor physical therapists will provide women with the same set of exercises and standard schedule of one initial visit and 3 follow up appointments. All other follow-up will be performed in the above-mentioned outpatient clinics.

There are no laboratory tests in this trial other than what would routinely be collected for the workup of SUI, nor is there involvement of any community advisory board. We do not perform urodynamic studies prior to managing patients with SUI with conservative therapy, so this study will not be performed. Also, there will not be any research conducted outside of the UNM HSC and its affiliates.

## **9. Resources Available**

[name] is a board certified subspecialist in Urogynecology and will serve as the primary investigator (PI) for this study. She is an experienced researcher at UNM and eligible PI at UNM. She has been the PI on multiple research trials and has successfully completed randomized control trials both as a fellow and now at UNM. Dr. [name] is the fellow who has a total of 12 months of protected research time during her fellowship in order to complete this study.

The University of New Mexico (UNM) urogynecology division operates at two main locations. UNM Eubank Urogynecology Clinic located in Northeast Albuquerque provides a full range of services for women with pelvic floor disorders. The Eubank clinic consists of 8 examination rooms, 2 treatment rooms, and 2 physical therapy rooms. Our second location is at Sandoval Regional Medical Center (SRMC), a community-based facility located in Rio Rancho, New Mexico, a large suburb located outside of Albuquerque.

Timeline	July 2018- Oct 2019	November 2019-Feb 2020	Mar 2017-May 2020
-----------------	----------------------------	-------------------------------	--------------------------

PROTOCOL TITLE: *SQEASI: Systematized Quality Exercise Alternatives for Stress Incontinence*

Subject recruitment, therapy, through 3 month follow up		
Data analysis		
Manuscript preparation		

Research Staff: The Urogynecology Division employs a program specialist, 3 research coordinators and one student research assistant. Our research staff has extensive experience conducting multi-center investigations and recruiting patients to clinical studies, with special expertise in community-based research and quality of life studies.

Research Experience: The Urogynecology Division at UNM has a strong history of conducting high quality research and collaboration with other investigators in the US and abroad, and has consistently met or exceeded recruitment goals on time. We have been members of the NICHD-sponsored PFDN, and have met recruitment goals with high rates of follow-up and accurate data collection. In addition to PFDN research, [name] has mentored and has been the PI on multiple clinical trials and contributes multiple publications in peer-reviewed journals. Her Curriculum Vitae is attached.

Our group is well versed in the importance of adherence to protocols, timely completion of regulatory requirements, effective recruitment strategies, and the importance of the inclusion of minority subjects. Research is integral to all aspects of Divisional work; importantly, all members of the clinical team participate in research efforts. There are weekly research meetings to discuss the progress of the ongoing studies within the department, and it is an excellent forum to ensure that all involved are adequately informed of their duties, of the protocol, and of the procedures.

We do not anticipate that emergency care will be needed for this study; the urogynecology physicians are available on a 24 hour basis, 7 days per week for their patients requiring emergency care.

## **10. Prior Approvals**

There will not be any approvals obtained prior to commencing the research. The study was presented to [name] for approval, and the signed Departmental Review Form can be found in the “supporting documents” section.

This study does not include any ionizing radiation, biological specimens, or drugs.

## **11. Multi-Site Research**

This is not a multi-site research study.

## **12. Study Procedures**

This non-blinded, non-inferiority randomized controlled trial will be conducted at the UNM Eubank Clinic and SRMC Urogynecology clinic. Each site will recruit participants and we will plan to obtain up to 75 between the two sites. Collaborating investigators will be members of the Urogynecology Division at UNM HSC.

The primary aim of our study is to determine if quality of life is improved with use PFPT versus home biofeedback therapy alone in women with SUI. The target population will be patients with SUI who are seeking care. The current recommendation is to advise patient undergo conservative management with PFPT, try an incontinence pessary, or request the patient perform exercises at home. For all patients who present for treatment of SUI, we will take a thorough history and physical (including a POP-Q pelvic examination), score vaginal muscle strength based on Modified Oxford Grading Scale, perform a cough stress test to assess for SUI, and counsel the patient on all of her options including medical and surgical interventions.

If the patient is interested in conservative management and fulfills study inclusion criteria, we will then offer her the choice of volunteering for the study. All women will give written consent prior to their enrollment at this time and fill out questionnaires in the clinic. Research staff and clinicians will obtain consent and administer study questionnaires. After enrollment, participants will fill out baseline surveys, including the International Consultation on Incontinence Questionnaire- Short form (ICIQ-SF), Incontinence Severity Index (ISI), European Quality of Life-5 dimensions (EQ-5D), Overactive Bladder Questionnaire short form (OAB-q SF) Pelvic Organ Prolapse Incontinence Sexual Questionnaire (PISQ-12), and Female Sexual Function Index (FSFI). Data collected in addition to the above outcome measures includes patient demographics, medical/surgical History, and contact information, which are attached as supporting documents. This information will be collected from the patient on the day of enrollment and we will review the patient's medical record if information is missing or unclear.

Randomization assignment will be generated by computer based randomization table and assigned by a research coordinator not otherwise involved in the study. Assignments will be kept in sealed opaque envelopes numbered sequentially. On the day of the patient's clinic visit, after signing consent and deciding to participate, the research coordinator will bring the next envelope in the sequence will be opened, randomizing the patient to PFPT or home biofeedback. The therapy allocation will then be carried out.

The biofeedback group will be given a PeriCoach® biofeedback device, which has a Bluetooth connection to a smartphone, free of charge. The smartphone application will be uploaded during the visit and linked to the device to ensure the patient understands how to

PROTOCOL TITLE: *SQEASI: Systematized Quality Exercise Alternatives for Stress Incontinence*

install the program. An information sheet with recommendation for exercise frequency will be given at the time of enrollment to provide recommendations for use. All participants will start as a beginner in the program and works up to a maintenance level. At the end we expect they will be doing 15 exercises, 3 times per day per manufacturer's instructions. 2 weeks following enrollment, these patients will be called to ensure they understand how device functions and are not having technical difficulties. When the patient returns for the 3 month follow up the smartphone app will be reviewed as the app records how often the patient performs the exercises. If that is not available, we will have the patient self-report her exercise frequency.

For patients randomized to physical therapy, PFPT will be scheduled for 4 sessions over 3 months, as is common practice for patients with SUI. These patients will receive instructions on how to engage their core, contract their vaginal muscles, as well as recommendations for home exercises to be performed for 3 sessions per day. The first session will be to establish the patient's baseline abilities with follow up sessions to reinforce instructions, performance of exercises and to ensure the patient is improving. Patient compliance of attending PT sessions will be recorded, as will the amount each patient spends in co-pays per session. After 3 months, regardless of the number of appointments the patient has attended, she will return for a follow up visit to assess how well she is doing.

Three months after starting active treatment, all participants will have a return visit to discuss progress, which is consistent with our standard care for these patients. If the participant had a delay in starting PFPT, the follow up visit will occur 3 months after first PT appointment. At the 3 month visit the patient will complete the ISI, ICIQ-SF, EQ-5D, OAB-q SF, PISQ-12, FSFI, and PGI-I. We will also ask the patient which treatment she would prefer if given the option, the level of satisfaction she has with the current treatment, and if she is planning any future surgical procedures or treatment for her stress incontinence. A physical exam will assess pelvic floor strength using the Modified Oxford Grading Scale and a cough stress test will be performed. If the patient is unable to return to clinic, a member of the research team will call the patient to administer the surveys over the phone. If unable to contact the patient 3 times, we will discontinue attempts and the patient will be considered lost to follow up.

Table 1: Outcomes collected at various time points

	Baseline	3 months
Demographic and medical history	X	
ISI	X	X
Revised Oxford Scale	X	X
ICIQ-SF	X	X
EQ-5D	X	X

FSFI	X	X
OAB-q SF	X	X
PISQ-12	X	X
PGI-I		X
Follow up Questionnaire		X

Our primary outcome is changes in QOL at 3 months after treatment initiation as measured by the ICIQ-SF. It is our standard of care to see patients back at 3 months following SUI treatment initiation to assess for continued leakage and offer further conservative or surgical management. Therefore, as part of a secondary aim we will assess sexual function, compliance with treatment between groups, preference between 2 options, and desire for further treatment at this 3 month time point.

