## 1. Objectives

The objective of this research is to perform a non-blinded, non-inferiority randomized controlled trial to assess the quality of life (QOL) of women with stress urinary incontinence (leakage of urine with cough or sneeze) before and after conservative treatment with either pelvic floor physical therapy (PFPT) or home biofeedback. The target population are patients with stress urinary incontinence (SUI) who are seeking care and desire non-surgical management. Our central hypothesis is that home biofeedback will be non-inferior to pelvic floor physical therapy and both will equally improve quality of life for women with stress urinary incontinence. The specific aims are:

**Aim 1:** To compare quality of life, as measured by the International Consultation Incontinence Questionnaire-Short Form (ICIQ- SF), in women with stress predominant incontinence before and after PFPT versus home biofeedback application after 3 months of therapy. Secondary outcomes related to this aim include improvements in urinary incontinence severity as measured by the Incontinence Severity Index (ISI) and desire to pursue additional therapy (such as pessary or surgery) at the conclusion of the study.

**Hypothesis:** Home biofeedback will demonstrate equal improvement in QOL in women with SUI compared to PFPT.

**Aim 2:** To perform a comparative analysis of cost between PFPT treatment and home biofeedback for stress predominant incontinence as well as patient preference for either PFPT vs home biofeedback. **Hypothesis:** Home biofeedback will be less expensive than PFPT due to decreased copays, driving to visits, with similar success rates and women will prefer to have home therapy.

**Aim 3:** To determine whether patients experience improvement in sexual function following treatment using the Pelvic Organ Prolapse Incontinence Sexual Questionnaire- 12 and Female Sexual Function Index (FSFI). **Hypothesis:** Both groups will report improved sexual function.

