### **4. Inclusion and Exclusion Criteria**

We will recruit patients who present to the University of New Mexico Urogynecology and Gynecology practices at UNM Eubank Clinic (UNM) or Sandoval Regional Medical Center (SRMC) with pure stress urinary incontinence or mixed urinary incontinence with stress predominant symptoms who have never had an anti-incontinence procedure in the past or formalized PFPT. They also cannot be currently using a pessary. To confirm diagnosis and eligibility, we will conduct a history and physical, complete with cough stress test and POP-Q pelvic examination. A cough stress test requires the patient to cough or Valsalva in lithotomy or standing position to assess for leakage of urine and is part of our routine standard of care when evaluating urogynecologic issues. Urinary leakage during this test indicates SUI. If the patient notes >50% of incontinence symptoms from SUI, she will be introduced to the study and provided with written information that may help her decide if participation in the study is right for her. All patients will be counseled about possible treatment options for stress urinary incontinence including non-surgical and surgical techniques. If a woman declines to participate

PROTOCOL TITLE: *SQEASI: Systematized Quality Exercise Alternatives for Stress Incontinence*

or is withdrawn from the study either by her desire or that of the research staff, she will be offered the same treatment options. Her follow up appointments will be the same regardless of participation in the study.

The rationale for targeting this population is that these are women who would routinely undergo conservative management for their condition initially. Patients will be enrolled if they meet the inclusion and do not meet the exclusion criteria.

The inclusion criteria are:

- Female Subjects >18 years of age
- SUI or Mixed UI with stress predominant symptoms and more bother by the SUI
- English speaking/reading
- Own a smartphone that can support phone application and Bluetooth for the biofeedback device and be able to upload a smartphone application with minimal instruction
- Willing to come for 4 PFPT visits over 3 months if randomized

Exclusion criteria:

- Prior anti-incontinence surgery
- Had prior pelvic floor physical therapy for SUI
- Prolapse of any compartment noted below the hymen
- Inability to speak/understand English
- Pregnant
- Decline or unable to return for frequent PT visits during study period

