**PROTOCOL TITLE: SQEASI: Systematized Quality Exercise Alternatives for Stress Incontinence**

personally benefit by participating in this research study. Women who are randomized to at home biofeedback will potentially get benefit from having a personal device they can keep. Participation in this study may provide information that may help other people who have a similar medical problem in the future. The literature supports improvement of QOL with improved SUI. PFPT and biofeedback have both been successfully used to treat SUI in the past.

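### Preference is asked only after 3 months on one allocated, unmasked treatment, so Aim 2's hypothesis that women prefer home therapy cannot be tested free of allocation effects, and the named Fisher test does not address it.

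*Combined protocol and SAP*

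**What the plan says.** Section 1 makes "patient preference for either PFPT vs home biofeedback" part of Aim 2 and attaches a directional hypothesis: home therapy will be cheaper, "with similar success rates and women will prefer to have home therapy". It gives no reference proportion.

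Section 12 describes parallel groups, the envelope "randomizing the patient to PFPT or home biofeedback", with no crossover. At the 3-month visit, "We will also ask the patient which treatment she would prefer if given the option". The same section places "preference between 2 options, and desire for further treatment at this 3 month time point" under a secondary aim. The baseline surveys it lists contain no preference item, and Table 1 marks the Follow up Questionnaire at 3 months only.

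The arms differ in what they are given. Section 19 says "Women who are randomized to at home biofeedback will potentially get benefit from having a personal device they can keep". Section 22 assigns the cost of the four PFPT sessions, and of travel to them, to the participant or her payer.

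Section 4 excludes women with prior PFPT for SUI and those who "Decline or unable to return for frequent PT visits during study period", and requires a suitable smartphone. Section 7 lists preference as exploratory. Section 13 names Fisher's exact test for categorical variables, between and within groups, and says nothing specific about preference.

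**The concern.** A preference stated after 3 months on a known treatment is a post-randomisation outcome. It can reflect what the woman wanted beforehand, familiarity with what she received, how well it worked and, in one arm, ownership of a free device. With no answer from before allocation, the data cannot separate these components.

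The analysis adds a second difficulty. Whether most women prefer home therapy is a question about one proportion against a reference such as 50%. A between-arm Fisher test compares two proportions with each other. A within-group comparison over time is not available, because preference is recorded at one time point only.

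At stake is the interpretation of the preference part of Aim 2. A significant between-arm result could be read as support for home therapy when it shows only that women lean towards what they were given, and a null result could hide a real majority. The primary ICIQ-SF comparison is not affected.

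**Working it through.** **Inputs.** The plan states no figure for preference, so there is none to reproduce. The 21 evaluable women per group (42 in total; sections 5 and 13) were set for the ICIQ-SF and serve here only as the number answering. A two-sided 0.05 level is assumed. All preference proportions below are illustrative assumptions, not document figures. Write pB and pP for the proportions naming home therapy in the biofeedback and PFPT arms.

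**1. Fisher's exact test between arms, 21 per arm.** Rejection probability = sum over (i, j) of Bin(i; 21, pB) × Bin(j; 21, pP), taken over tables with Fisher p ≤ 0.05.

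| Situation | pB | pP | Overall | Rejects |
|---|---|---|---|---|
| No preference, no leaning | 0.50 | 0.50 | 0.50 | 2.0% |
| No overall preference, 70% name what they received | 0.70 | 0.30 | 0.50 | 62.9% |
| True 70% home preference in both arms | 0.70 | 0.70 | 0.70 | 2.3% |

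The test responds to leaning towards the allocated arm and is almost blind to the majority that Aim 2 hypothesises.

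**2. Pooled proportion against 50%, n = 42.** The exact two-sided test needs at least 28/42 (66.7%). Power, P(X ≥ 28), is 74% at a true 70% and 92% at a true 75%. A workable test of the hypothesis therefore exists, although the plan does not specify it.

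**3. Unequal completion alone.** Take indifferent women, 70% of whom name what they received. Pooled home proportion = (nB × 0.7 + nP × 0.3)/(nB + nP).
- 25 and 25 completers: 25/50 = 50%.
- 25 biofeedback and 18 PFPT: (17.5 + 5.4)/43 = 53.3%.
- 18 biofeedback and 25 PFPT: (12.6 + 7.5)/43 = 46.7%.
- A 90% leaning with 25 and 18: (22.5 + 1.8)/43 = 56.5%.

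All are well below the 66.7% needed to reject. Imbalance on its own does little.

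**4. Asymmetric leaning, 21 per arm.** The women are again indifferent, but the pull towards home therapy in the biofeedback arm is stronger than the pull towards PFPT in the other. False declaration of home preference = P(XB + XP ≥ 28), with XB ~ Bin(21, pB) and XP ~ Bin(21, pP).
- 80% and 40%: pooled (0.8 + 0.4)/2 = 60%; false declaration about 21%.
- 90% and 40%: pooled (0.9 + 0.4)/2 = 65%; about 47%.

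A free device in one arm against paid visits in the other makes some asymmetry plausible. Nothing collected under the plan could show or exclude it.

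**The case against.** A reader might infer that the hypothesis cannot be tested at all, or that Aim 2 is left unanswered, because no woman tries both options. The documents do not support that. Stating a preference does not require experience of both treatments; section 12 has every patient counselled on all her options, and every woman followed up is asked. Step 2 shows that a pooled test has reasonable power for a large majority. Preference after experience of one treatment is also a legitimate quantity, and section 7 frames it that way. This objection stands.

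It can also be said that no section plans a pooled analysis, and that unequal completion barely moves a pooled figure. Both are correct. What remains is the asymmetric case, and the fact that the one named method, used between arms, answers a different question.

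A third objection is that a baseline answer comes from women who have tried neither treatment, and who may know that the study supplies the device free. That is fair, and it is why the baseline answer should not replace the 3-month answer as the only Aim 2 result. Which of the two matters more is a choice of estimand.

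Two further inferences go beyond the documents. One is that the attendance criterion removes the women most likely to prefer home therapy: plausible, but undocumented. If true, it would work against the hypothesis, and the smartphone requirement may select the other way. The other is that baseline preference is needed to interpret the ICIQ-SF result; no planned analysis rests on it, and at about 21 per arm a preference-by-arm analysis would be very imprecise.

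**Conclusion.** The point holds in a limited form. Preference is recorded only after allocation and treatment, so the answer combines underlying preference with allocation effects that the data cannot separate. The hypothesis is testable, but not free of those effects, and the plan names no analysis that addresses it.

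The size depends on assumed leanings. At 21 per arm, the between-arm Fisher test rejects in about 63% of trials with no overall preference (70% versus 30%) and in about 2% with a true 70% preference in both arms. A pooled test is little affected by unequal completion (47% to 53% in the example), but an 80%/40% asymmetry in indifferent women would give about 21% false declarations. Whether such asymmetry would occur is unknown.

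Severity is low. Section 7 labels preference exploratory, although section 1 gives it a hypothesis and section 12 places it under a secondary aim. The Follow up Questionnaire is not reproduced in the document, so its exact wording and response options cannot be judged.

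**What to change.** - Add one item (PFPT, home biofeedback, no preference) to the baseline forms and to Table 1, completed after counselling and consent and before the envelope is opened. Use the same item at 3 months.
- In section 13, report the baseline proportion preferring home therapy with an exact confidence interval, read against 50%. State in advance whether answers of no preference stay in the denominator.
- Report the 3-month answer by arm, with shift from baseline. Present the two time points as distinct quantities: informed choice before treatment, and preference after experience of one option. A between-arm test, if kept, should be described as testing the effect of allocation on preference.
- State that the result applies to smartphone-owning women willing to attend PFPT.
- Give preference the same endpoint level in sections 1, 7 and 12.

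The cost is one extra question at enrolment and an IRB amendment. The baseline answer reflects no experience of either treatment, which is why both time points are kept. The item has to be in place before women are randomised, since a pre-allocation answer cannot be recovered reliably afterwards.
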